4.3 Re-screening if patient does not meet inclusion/exclusion criteria first time around

If a patient does not meet the inclusion/exclusion criteria initially he can be re-screened, provided it is still possible to complete re-screening and study treatment before the patient's standard of care prostatectomy.

4.4 Patient registration procedure

Potential participants will be identified from patients referred to the Oxford University Hospitals Urology MDT for the management of localised prostate adenocarcinoma, and will be given a recruitment flyer. Patients opting for surgical management will be considered for the trial with an initial approach made to the patient by the patients clinical care team.

Following the initial approach and confirmation of interest in the study, patients will be informed of the aims of the trial, and will be given a Patient Information Sheet (PIS) and have the opportunity to ask questions. Patients who express interest will be contacted e.g. by telephone approximately 24 hours later by a member of the clinical care team and if still interested will be scheduled to attend to provide written informed consent and conduct screening procedures. If potential participants do not meet the screening criteria they will not be able to continue on the study and this will be communicated to them.

A screening log must be kept of all patients considered for the trial including any that are subsequently excluded; the reason for exclusion must be recorded on this form. A copy of the screening log should be sent to the trial office on request, but without patient identifiers. The original must be retained on site.

Before entering a patient onto the study the Principal Investigator or designee will confirm eligibility. If in any doubt the Chief Investigator must be consulted before entering the patient.

Details of the query and outcome of the decision must be documented on the registration/eligibility checklist.

On completion of consent and screen procedures (i.e. before first xentuzumab treatment), site staff will complete the trial registration form and email this to the trial office to confirm the patient's eligibility: [contact]

The trial office will check the information provided and register the patient on the trial. The patient's trial number will then be confirmed by return email to the trial site staff.

4.5 Trial assessments and procedures

Please refer to the Schedule of Events given at the front of this protocol. Details of all protocol evaluations and investigations must be recorded in the patient's medical record for extraction onto the CRF. All study visits will take approximately 2-3 hours, comfort breaks will be provided during this time.

4.6 Informed consent

Potential participants will be given a current, approved version of the Patient Information Sheet and consent form. They will also receive clear verbal information about the study detailing no less than: the nature of the study; the implications and constraints of the protocol; the known side effects and any risks involved in taking part. It will be explained that they will be free to withdraw from the study at any time, for any reason, without prejudice to future care, and with no obligation to give a reason for withdrawal. They will have at least 24 hours to consider the information provided and the opportunity to question the Investigator, their GP or other independent parties before deciding whether to participate.

The Investigator who obtains consent must be suitably qualified and experienced. All delegates must be authorised by the Principal Investigator to obtain consent. The Investigator is responsible for ensuring that the trial consent procedures comply with current applicable GCP Regulatory and ethical requirements. Informed consent discussions and outcomes must be well documented in the medical record. The Investigator must be satisfied that the patient has made an informed decision before taking consent. The patient and the Investigator must personally sign and date the current approved version of the informed consent form in each other's presence. A copy of the information and signed consent form will be given to the participant. When completed 4 copies of the consent form are required: 1 for the patient; 1 for Investigator Site File and 1 (original) to be kept in the patient's medical notes (at the discretion of the treating hospital) and 1 for the Biobank.

Contraceptive/ Pregnancy counselling

All participants must be advised on the need to use reliable methods of contraception during the study. The advice should include:

- (1) The acceptable methods, required for trial subjects with premenopausal female partners, include: condom plus spermicide for the participating male plus another acceptable form of birth control for female partners e.g. female sterilization, implants, injectables, combined oral contraceptives, some intrauterine devices (IUDs). Abstinence is an acceptable method only when this is in line with the preferred and usual lifestyle of the subject.
- (2) These precautions should be continued for minimum 3 months after the last dose of study drug.
- (3) That any pregnancy in female partners of male trial subjects occurring within 70 days of the last administration of study drug should be notified by the trial participant to the study team. The outcome (spontaneous miscarriage, elective termination, normal birth or congenital abnormality) will be reported and followed up even if the participant is discontinued from the study.

4.7 Pre-dosing evaluations

The following screening and eligibility assessments must be performed/obtained within the 7 days before the patient receives the first study dose, except where indicated otherwise below.

- Written informed consent
- Demographic details (age, sex, smoking status and self-reported race/ethnicity)
- Medical History: to include current symptoms, cancer history, prior cancer therapies and procedures, reproductive status, smoking history, and clinically significant disease history and concomitant diseases
- Concomitant medications
- Physical examination, which should be symptom driven and include general appearance, examination of cardiovascular system, chest and abdomen. Any abnormality identified at baseline should be recorded
- Height, weight, ECOG performance status (to confirm eligibility) (Appendix 1)
- Vital signs: systolic /diastolic blood pressure (BP), pulse rate and temperature
- Haematology: Hb, white blood cells (WBC) with differential count (neutrophils and lymphocytes) and platelets
- Biochemistry: sodium, potassium, calcium, phosphate, urea, creatinine, total protein, albumin, bilirubin, alkaline phosphatase (alk phos), AST and ALT, LDH and glucose
- Blood PSA, insulin, HbA1c and IGF-1

- Electrocardiogram (ECG) to confirm fitness for treatment
- Presence of prostate adenocarcinoma on prostate biopsy*
- Confirm availability of surplus tissue from diagnostic biopsy

*Standard of care imaging assessments need not be completed in the 7 day screening period.

4.8 Evaluations during the study

Evaluations on day 1

On the day the first dose of xentuzumab is given:

- Current symptoms, assessment for adverse events
- Concomitant medications
- Physical examination as detailed in 5.2.
- Vital signs: BP, pulse, temperature
- Haematology: Hb, WBC with differential count (neutrophils and lymphocytes) and platelets
- Biochemistry: sodium, potassium, calcium, phosphate, urea, creatinine, total protein, albumin, bilirubin, alkaline phosphatase (alk phos), AST and ALT, LDH and glucose
- Blood PSA, insulin, HbA1c, IGF-1
- Research blood samples
- Xentuzumab infusion: to commence after blood has been taken for the above assessments. Xentuzumab infusion can then be started without waiting for the day 1 blood results, provided the screening blood tests were taken within the 7 days pre-cycle 1. The infusion is to be administered over 1 hour (with up to 15 minutes extra if needed for staff time to end infusion). Record time of starting and completing infusion. Patient to be monitored during the infusion and for one hour after the end of infusion. Grade 1 to 2 infusion reactions will be managed by reducing the infusion rate to 2 hours. For symptomatic treatment of infusion reactions hydrocortisone, antihistamines such as chlorphenamine, an antipyretic/analgesic, and/or a bronchodilator may be administered. Severe reactions require immediate and permanent discontinuation of xentuzumab infusion.

Evaluations on day 8 (+/- 1 days)

- Assessment for adverse events
- Concomitant medications
- Vital signs: BP, pulse, temperature
- Haematology: Hb, WBC with differential count (neutrophils and lymphocytes) and platelets
- Biochemistry: sodium, potassium, calcium, phosphate, urea, creatinine, total protein, albumin, bilirubin, alkaline phosphatase (alk phos), AST and ALT, LDH and glucose
- Xentuzumab infusion: administered over 1 hour (may be slowed to 2 hours if required due to infusion reaction, with up to 15 minutes extra if needed for staff time to end infusion). Monitor patient during infusion and for at least 15 minutes after end of infusion as is standard practice. Record time of starting and completing infusion. At clinical discretion patient may then leave if there are no symptoms of infusion reaction, or continue to monitor as appropriate.

Evaluations on day 15 (+/- 1 days)

- Assessment for adverse events
- Concomitant medications
- Vital signs: BP, pulse, temperature
- Weight

- Physical examination as detailed in 5.2.
- ECOG performance status
- Haematology: Hb, WBC with differential count (neutrophils and lymphocytes) and platelets
- Biochemistry: sodium, potassium, calcium, phosphate, urea, creatinine, total protein, albumin, bilirubin, alkaline phosphatase (alk phos), AST and ALT, LDH and glucose
- Blood PSA, insulin, HbA1c, IGF-1
- ECG
- Xentuzumab infusion: administered over 1 hour (may be slowed to 2 hours if required due to infusion reaction, with up to 15 minutes extra if needed for staff time to end infusion). Monitor patient during infusion and for at least 15 minutes after end of infusion as is standard practice. Record time of starting and completing infusion. At clinical discretion patient may then leave if there are no symptoms of infusion reaction, or continue to monitor as appropriate.

Evaluations on day 22 (+/- 1 days) It is acceptable for this visit to be missed for participants whos surgery takes place within 6 days of the 3rd dose

- Assessment for adverse events
- Concomitant medications
- Vital signs: BP, pulse, temperature
- Haematology: Hb, WBC with differential count (neutrophils and lymphocytes) and platelets
- Biochemistry: sodium, potassium, calcium, phosphate, urea, creatinine, total protein, albumin, bilirubin, alkaline phosphatase (alk phos), AST and ALT, LDH and glucose
- Xentuzumab infusion: administered over 1 hour (may be slowed to 2 hours if required due to infusion reaction, with up to 15 minutes extra if needed for staff time to end infusion). Monitor patient during infusion and for at least 15 minutes after end of infusion. Record time of starting and completing infusion. At clinical discretion patient may then leave if there are no symptoms of infusion reaction, or continue to monitor as appropriate.

Evaluations on day 29 (+/- 1 days, participants whose surgery is taking place after day 29 only)

- Assessment for adverse events
- Concomitant medications
- Vital signs: BP, pulse, temperature
- Haematology: Hb, WBC with differential count (neutrophils and lymphocytes) and platelets
- Biochemistry: sodium, potassium, calcium, phosphate, urea, creatinine, total protein, albumin, bilirubin, alkaline phosphatase (alk phos), AST and ALT, LDH and glucose
- Xentuzumab infusion: administered over 1 hour (may be slowed to 2 hours if required due to infusion reaction, with up to 15 minutes extra if needed for staff time to end infusion). Monitor patient during infusion and for at least 15 minutes after end of infusion. Record time of starting and completing infusion. At clinical discretion patient may then leave if there are no symptoms of infusion reaction, or continue to monitor as appropriate.

Evaluations on day 36 (+/- 1 days, participants whose surgery is taking place after day 36 only) - Where prostatectomy is unexpectedly delayed beyond day 36, patients will continue to be dosed with weekly xentuzumab to within 6 days of surgery, up to a maximum of 10 doses in total

- Assessment for adverse events
- Concomitant medications
- Vital signs: BP, pulse, temperature

- Haematology: Hb, WBC with differential count (neutrophils and lymphocytes) and platelets
- Biochemistry: sodium, potassium, calcium, phosphate, urea, creatinine, total protein, albumin, bilirubin, alkaline phosphatase (alk phos), AST and ALT, LDH and glucose
- Xentuzumab infusion: administered over 1 hour (may be slowed to 2 hours if required due to infusion reaction, with up to 15 minutes extra if needed for staff time to end infusion). Monitor patient during infusion and for at least 15 minutes after end of infusion. Record time of starting and completing infusion. At clinical discretion patient may then leave if there are no symptoms of infusion reaction, or continue to monitor as appropriate.

Evaluations 1-3 days before surgery (Day 23 - Day 41), non-fasting

- Assessment for adverse events
- Concomitant medications
- Vital signs: BP, pulse, temperature
- Weight
- ECOG performance status
- Physical examination as detailed in 5.2.
- ECG to confirm fitness for surgery
- Haematology: Hb, white blood cells (WBC) with differential count (neutrophils and lymphocytes) and platelets
- Biochemistry: sodium, potassium, calcium, phosphate, urea, creatinine, total protein, albumin, bilirubin, alkaline phosphatase (alk phos), AST and ALT, LDH, glucose.
- Blood PSA, insulin, HbA1c & IGF-1
- Research blood samples, NB take blood same time of day (± 3 hr) as Day 1 sample.

Day of surgery (day 24 – 42 unless surgery has been delayed)

Standard of care radical prostatectomy with collection of research tissue samples:

- Core biopsies (2-3) taken in theatre from radical prostatectomy for immediate fixation.
- Fresh frozen punch biopsy from index tumour processed fresh or stored as listed in section 6.1 for later analysis.

4.9 End of Study (EoS) evaluations at 6 weeks after surgery (± 7 days)

- Assessment for adverse events
- Concomitant medications
- Vital signs: BP, pulse, temperature
- ECOG performance status
- Physical examination as detailed in 5.2
- Haematology: Hb, WBC with differential count (neutrophils and lymphocytes) and platelets
- Biochemistry: sodium, potassium, calcium, phosphate, urea, creatinine, total protein, albumin, bilirubin, alkaline phosphatase (alk phos), AST and ALT, LDH, glucose.
- Blood PSA, insulin, HbA1c and IGF-1

Follow-up evaluations

There is no long-term follow-up as part of the trial. Further follow-up for trial purposes will only be completed if a participant has an ongoing drug-related AE that is related to trial participation at the end of study visit, or if participant's female partner has become pregnant. Participants will otherwise be followed-up post the end of study visit as per standard care post-prostatectomy.

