Cancer remains a fatal disease that continues to kill far more patients daily than COVID-19. The need to identify better treatments through clinical research is not affected by the presence of the pandemic. Pausing such research for months, if not years, until the pandemic subsides will likely result in more deaths as improvements in care are delayed. Nevertheless we have put in place significant mitigations. The COVID-19 risk for potential patients has been minimised as much as possible. The WINGMEN recruitment site, Churchill Hospital, is nominally COVID-19 free, and infected or potentially infected patients are treated at a geographically distinct site (the John Radcliffe Hospital). The following procedures have also been put in place at site:

- All patients (in and outpatients) are screened upon entry to the Churchill site
- Human traffic at the Churchill site is minimal with face to face appointments avoided and staff working from home, whenever possible.
- Face masks/social distancing/level 1 PPE for patient examinations and other protective measures are mandatory for staff at the Churchill site

Furthermore, this trial requires only 6 extra patient visits: screening, 4 treatment visits (unless surgery is unexpectedly delayed) and one visit after completion of treatment and before surgery, for post-treatment blood tests. The post-treatment End-of-Study trial assessment will be held on the same day as the routine 6-week post-operative assessment, and so will not involve an extra hospital visit. There is no evidence that treatment with an IGF inhibitory drug will cause patients to be immunosuppressed. Indeed, given experimental evidence that IGFs themselves can suppress the immune system, it is possible that treatment with xentuzumab could enhance immune responses. Therefore, we accept that extra hospital visits may confer additional COVID risk, but the treatment itself should not increase this risk.

Covid 19 Vaccination Considerations

There is no contraindication to having a COVID-19 vaccination before, during or after the study and participants will be encouraged to do so.

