9 DRUG MANAGEMENT

9.1 Drug supplies

Xentuzumab is supplied as liquid formulation containing xentuzumab 10 mg/mL in 20 ml in individually boxed vials (200 mg xentuzumab/vial). The excipients are L-Histidine/L-Histidine hydrochloride monohydrate, mannitol, sucrose, polysorbate 20, and water for injection.

Xentuzumab will be supplied free of charge by Boehringer Ingelheim KG and QP released to Almac who will do a second QP release to site pharmacy.

Any required supportive medication is to be sourced and funded locally.

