## 5.5 Treatment Compliance with Details of Intervention

The intervention being assessed in this trial is the IMP xentuzumab (Boehringer Ingelheim), an insulin-like growth factor (IGF) neutralising antibody. The drug is administered by intravenous infusion over one hour, once weekly for 4 weeks prior to standard of care radical prostatectomy. Trial subjects whose surgery is delayed will continue to receive weekly xentuzumab for up to 10 cycles in total. The final dose must be given within 6 days of surgery.

Compliance and adherence to the protocol will be assessed by:

- Ability to attend for trial treatment on a weekly basis  $\pm$  1 day of scheduled treatment visits. Incidence of delayed cycles and reasons for delay will be recorded as in WINGMEN\_DataDefinitions&Tables Section 4.2 and Table 5.
- Ability and agreement to provide samples of blood and tissue for research.
- Attendance for a post-xentuzumab blood sample (1-3 days before surgery) at the same time of day and interval after last meal ( $\pm$  2-3 hr) as the pre-xentuzumab blood sample. This is important for consistency of metabolomic profiling.

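### The pre-surgery visit is timed from surgery alone, so on some surgery days its post-treatment blood, laboratory tests and ECG can fall on or before the day of the final infusion

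*Protocol*

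**What the plan says.** Protocol 4.8 sets the visit at "Evaluations 1-3 days before surgery (Day 23 - Day 41), non-fasting". It supplies research blood, PSA, insulin, HbA1c, IGF-1, routine haematology and biochemistry, and an ECG. The Schedule of Events labels the same visit as the day before surgery. Neither place gives an interval after the last infusion.

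Surgery is planned as "Day of surgery (day 24 – 42 unless surgery has been delayed"). Beyond the four doses on days 1, 8, 15 and 22, Protocol 4.8 adds "Evaluations on day 29 (+/- 1 days, participants whose surgery is taking place after day 29 only") and "Evaluations on day 36 (+/- 1 days, participants whose surgery is taking place after day 36 only"), each with an infusion. Protocol 7.3 repeats the day 29 rule and requires the final dose within 6 days of the prostatectomy.

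Protocol 1.4, in its COVID-19 paragraph, counts this visit as "one visit after completion of treatment and before surgery, for post-treatment blood tests". SAP 5.5 lists, as a compliance item, "Attendance for a post-xentuzumab blood sample (1-3 days before surgery"), matched to the pre-treatment sample on time of day and interval since the last meal. Only the Day 1 text orders blood and infusion: "Xentuzumab infusion: to commence after blood has been taken for the above assessments". SAP 4.1.3 compares single-value circulating markers PRE and POST, and SAP 6 plans to correlate tissue inhibition with the tertiary endpoints.

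**The concern.** The infusion calendar runs forward from day 1 and the visit is counted back from surgery. Nothing in the operative text keeps the visit behind the last infusion, although Protocol 1.4 says that it comes after treatment has finished.

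Two things follow. First, the POST circulating values may mix draws taken before, on the day of, and after the final infusion. A blood–tissue correlation would then pair some men's blood from before the last dose with tissue from after it. The plan already controls draw timing for time of day and meals, but not for time since a 1000 mg infusion. Second, for a man whose visit falls on or before the final dose day, no scheduled trial laboratory test falls on a later day until the end-of-study visit about 6 weeks after surgery, and that visit has no ECG.

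**Working it through.** **Inputs**
- Surgery day S: 24 to 42 (Protocol 4.8), so 42 − 24 + 1 = 19 calendar days.
- Visit days: S − 3 to S − 1, printed range day 23 to 41 (Protocol 4.8).
- Nominal doses: days 1, 8, 15, 22; day 29 if S > 29; day 36 if S > 36; ±1 day at each visit after day 1 (Protocol 4.8, 7.3).
- Final dose at most 6 days before surgery (Protocol 5.1, 7.3).

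**1. The printed visit range.** 24 − 1 = 23 and 42 − 1 = 41, so the range reproduces with a one-day offset. With the full 1–3 days it would be 24 − 3 = 21 to 42 − 1 = 41. The printed lower limit therefore fits the Schedule label (day before surgery) but not the words beside it.

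**2. Nominal doses.** For each S, let L be the last scheduled dose day before S. Compare each visit day with L, keeping the printed floor of day 23.

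| Surgery day S | Final dose L | Permitted visit days | Position relative to L |
|---|---|---|---|
| 24–29 | 22 | within 23–28 | all after |
| 30 | 29 | 27, 28, 29 | before, before, same day |
| 31 | 29 | 28, 29, 30 | before, same day, after |
| 32 | 29 | 29, 30, 31 | same day, after, after |
| 33–36 | 29 | 30–35 | all after |
| 37 | 36 | 34, 35, 36 | before, before, same day |
| 38 | 36 | 35, 36, 37 | before, same day, after |
| 39 | 36 | 36, 37, 38 | same day, after, after |
| 40–42 | 36 | 37–41 | all after |

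Six of 19 surgery days allow a visit on or before the final dose day, and two of these (30 and 37) allow nothing later. If the 1–3 day wording overrides the printed floor, days 24 and 25 join them (visit days 21–22 and 22 against a day 22 dose), giving 8 of 19. With longer delay the day 30 pattern recurs at S = 44, 51, 58 and 65.

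For S = 29 and 36 the nominal final dose is 7 days before surgery, outside the 6-day limit. Moving it to day 23 or 30 meets the limit, and every visit day is still later.

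**3. The ±1 day dose window.**
- One day early: S = 30 with a day 28 dose leaves visit day 29 after it; S = 37 with a day 35 dose leaves visit day 36 after it.
- One day late: S = 24 (dose day 23), S = 31 (dose day 30) and S = 38 (dose day 37) then have no later visit day.

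**4. Does omitting the late dose resolve it within the plan's own rules?** No. For S = 30 the previous dose would be 30 − 22 = 8 days earlier (7 if given on day 23). For S = 37 it would be 37 − 29 = 8 (7 if given on day 30). Both exceed 6.

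**5. Illustration of the exposure gap.** Assume first-order decay with the half-life of about 6 days in Protocol 1.2, and level = Σ 2^(−(t − d)/6) over the doses given by time t. For S = 30, the level at surgery after doses on days 1, 8, 15, 22 and 29 is 0.035 + 0.079 + 0.177 + 0.397 + 0.891 = 1.578. Blood taken before the day 29 dose has level 0.972 (day 27), 0.866 (day 28) or 0.772 (day 29). The tissue/blood ratios are 1.578/0.972 = 1.62, 1.578/0.866 = 1.82 and 1.578/0.772 = about 2.05. For S = 28, where every draw follows the last dose, they are 0.71 (day 25) to 0.89 (day 27).

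**The case against.** The strongest reply has five parts.

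- **The overlap is not forced.** A reader might infer that for surgery on day 30 or 37 the sample has to precede the last infusion. It does not: the ±1 day window can place the dose a day earlier, and a same-day draw could follow the infusion because no order is set. This stands.
- **The sample is still post-xentuzumab.** Blood taken after four weekly doses is on-treatment blood, so the SAP label is not wrong and the PRE/POST comparison keeps a meaning. This stands. The direct conflict is with Protocol 1.4.
- **This is not the only POST blood.** PSA and insulin are also taken on day 15 and at end of study, and the Schedule, as extracted, appears to mark research blood at surgery. That mark may be a damaged table, and 4.8 lists no such draw, so it is a further item to reconcile.
- **A drug-level ratio is not a biomarker effect.** Protocol 1.4 reports plasma IGF bioactivity at the assay's detection limit at 450 mg weekly, below the trial dose. That marker may barely move, and the ratios in the working should be read as exposure only.
- **It is late.** SAP 3.4.4 reports that recruitment was completed by Q1 2023, so no visit rule can change past draws. This limits the remedy but does not remove it.

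Two further inferences are not supported. One is that formulation ingredients would appear as metabolite changes ("The excipients are L-Histidine/L-Histidine hydrochloride monohydrate, mannitol, sucrose, polysorbate 20, and water for injection"). The documents give no amounts, clearance times or metabolite panel, and the effect would need a same-day draw after the infusion. The other is that extending the Day 1 blood-before-infusion order to this visit would solve the problem. With nominal doses it would place every permitted draw for surgery on day 30 or 37 before the final infusion, contrary to Protocol 1.4 and with the largest modelled gap (about 2.05).

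**Conclusion.** The concern holds in limited form. Protocol 4.8 allows the visit to fall on or before the final infusion day, against the purpose stated in Protocol 1.4. On nominal dose days this is possible on 6 of 19 surgery days and leaves no later visit day on 2 of them. These are calendar days. Protocol 1.2 expects four doses in a 3.5–4 week window and calls further delay unlikely, and the documents do not say how many men had surgery on those days.

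The count rests on nominal dosing and the printed day 23 floor. The exposure ratios rest additionally on the first-order assumption.

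The consequences are confined to the exploratory circulating-marker comparisons, the blood–tissue correlations, and the pre-operative laboratory tests and ECG. A reader might extend the point to the primary endpoint, but its POST tissue is taken at surgery and is not affected. Because a stated rule conflicts with a stated purpose, and a check is still possible from recorded data, the plan should be changed.

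**What to change.** **Protocol.** Reconcile the Schedule of Events, the COVID-19 paragraph of 1.4, the pre-surgery, day 29 and day 36 text of 4.8, and 7.3 on the order of this visit and the final infusion. Include the printed day range and whether research blood is drawn at surgery. This point proposes no dosing or clinical rule.

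**SAP 4.1.3.** Classify each POST draw as before, on the same day as, or after the final infusion. Protocol 4.8 requires infusion start and end times to be recorded, and Protocol 6.2 requires the date taken on each research sample. Use draw times where they are held to order same-day draws. Report the number of men in each class. Repeat the circulating PRE/POST comparisons and the blood–tissue correlations using only draws after the final infusion. If the companion Data Definitions and Tables document, which was not available here, already defines the POST draw, cross-refer to it.

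**Cost.** One derived variable and a small sensitivity analysis. Fewer men enter that analysis, so its estimates will be less precise. Same-day draws without a recorded time cannot be ordered and would be left out of it.
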